### 3. Investigational Plan

#### 3.1 Summary of Study Design

This is a multicenter, open-label study of rovalpituzumab tesirine in subjects with DLL3-expressing advanced solid tumors. The study will include 7 cohorts of subjects with the following cancers:

1. Malignant melanoma
2. Medullary thyroid cancer (MTC)
3. Glioblastoma
4. Large cell neuroendocrine carcinoma (LCNEC) of any origin
5. Neuroendocrine prostate cancer (NEPC)
6. High-grade gastroenteropancreatic neuroendocrine carcinoma (GEP NEC)
7. Other neuroendocrine carcinoma (NEC) and high grade neuroendocrine tumors (NET)
8. Solid tumors other than the above

As of protocol version 4.0, cohort 3 (Glioblastoma) is closed to enrollment. Specific guidance for cohort 3 (Glioblastoma) subjects (protocol version 3.0) are provided in Appendix 13.3.

Each disease-specific cohort will include two parts:

- Part A – Dose-Regimen Finding: Will involve disease-specific dose escalation, and possible dose-interval modification, to define the maximum tolerated dose (MTD) and/or possible recommended Phase 2 dose(s) (RP2Ds).
- Part B – Expansion Cohorts: Disease-specific expansion cohorts may be enrolled. Subjects in the expansion cohorts will be treated with a dose regimen(s) at or below the MTD and/or RP2D determined in Part A.

Dose limiting toxicities (DLTs) will be assessed during the DLT Evaluation Period (Section 3.1.3) for subjects in Part A, the dose regimen finding portion of the trial.

Safety will be monitored throughout the trial by the Safety Monitoring Committee (SMC) consisting at least of a Medical Monitor, Investigators, and the study biostatistician. The SMC will meet routinely to review the emerging safety, select pharmacodynamic and efficacy data, and may make dose-escalation and dosing-interval recommendations. The SMC may recommend further evaluation of safety at a given dose level, investigation of alternative dose regimens, including a dose level that is intermediate to the planned dose levels, modification of the dosing interval, limitation to the maximum number of doses, and/or elimination or cancellation of a dose level(s) in a cohort based on the experience in other cohorts. The SMC will also review cumulative safety data in order to identify safety concerns that may emerge due to cumulative exposure beyond the DLT window. The process for dose-escalation decisions and dose-interval recommendations, and the roles and responsibilities of the SMC may be detailed separately.

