**Figure 3-1 Dose-Escalation Decision Summary**

During 3+3 dose escalation, DLTs will be assessed during the DLT Evaluation Period (Section 3.1.3). If 0 of 3 subjects experience a DLT in a cohort, the next dose level will be opened for enrollment. If  $\geq 2$  of 3 subjects in a cohort experience a DLT, the MTD will have been exceeded and dose escalation will stop. If 1 of 3 subjects in a cohort experiences a DLT, an additional 3 subjects will be treated at that same dose level for a total of 6 subjects. If none of the 3 additional subjects experiences a DLT (1 of 6 subjects with a DLT), dose escalation will continue to the next higher dose level. If 1 or more of the 3 additional subjects experiences a DLT ( $\geq 2$  of 6 subjects with a DLT), the MTD will have been exceeded and dose escalation will not continue. Subjects who do not complete the DLT-evaluation period due to non-DLT reasons will not be considered DLT-evaluable and will be replaced for the DLT evaluation.

The MTD and RP2D will be determined by the Sponsor in consultation with the SMC after a review of all available data. At least 6 subjects must be treated at the putative MTD or RP2D, with no more than 1 incident of DLT.

If 3 or more disease-specific cohorts clear the 0.3 mg/kg or 0.4 mg/kg dose level and the Q6wk schedule, then the SMC may evaluate all the data available to determine an appropriate RP2D and the Part B expansion may proceed for all the cohorts in the study at these dose(s) and schedule.

During dose escalation, additional subjects may be enrolled at a dose level previously declared to be tolerated in order to explore further the safety and tolerability of the regimen. For instance, if

all 3 or 6 subjects necessary for DLT evaluation have been enrolled in a cohort, but have not yet completed the DLT evaluation period, additional subjects may be enrolled at a lower dose level(s), with approval of the Medical Monitor and Sponsor.

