### 3.1.3 Definition of Dose-Limiting Toxicities

The DLT evaluation period is the first 3 weeks of the first cycle of treatment for all subjects in Part A. DLTs are defined as any of the following in the DLT evaluation period, graded according to the National Cancer Institute’s Common Terminology Criteria for Adverse Events (NCI CTCAE), version 4.03:

- Grade 4 thrombocytopenia (or Grade 3 thrombocytopenia with bleeding) lasting more than 7 days and/or requiring platelet transfusion
- Grade 4 neutropenia lasting more than 7 days, and/or requiring hematopoietic growth factor rescue, or any febrile neutropenia (Grade 3 or 4 neutropenia with concurrent fever  $\geq 38.3^{\circ}\text{C}$ )
- Grade 4 anemia unrelated to underlying disease
- Clinically-significant Grade 3 or 4 non-hematologic laboratory abnormality that does not resolve to Grade 0/1 or baseline within 7 days
- Grade 3 or 4 non-laboratory AE with the exception of fatigue, asthenia, nausea, or other manageable constitutional symptom

The following events will not be considered DLTs:

- Any AE  $\geq$  Grade 3 clearly determined to be unrelated to study drug (e.g., PD)
- $\geq$ Grade 3 isolated alkaline phosphatase, amylase or lipase laboratory abnormality of any duration

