
 
• Grade 3 serosal effusions (pleural effusions, pericardial effusions, and ascites) and edema
 
• Grade 2 capillary syndrome
 
• Grade 4 thrombocytopenia/ Grade 3 thrombocytopenia with bleeding/ Need for platelet transfusion
 
• Grade 4 febrile neutropenia
 
• Grade 4 (<math>>20.0 \times \text{ULN}</math>) ALT or AST or Grade 3 (<math>>5.0\text{--}20.0 \times \text{ULN}</math>) ALT or AST elevation with concomitant total bilirubin Grade 2 or higher (<math>>1.5 \text{ULN}</math>)
 
• Grade 3 or higher hypoalbuminemia (<math><2 \text{g/dL}</math>)
 
• Grade 2 pneumonitis
 
	

Toxicities Requiring Discontinuation of Investigational Product at First Occurrence

• Grade 4 photosensitivity or skin reaction (Section 5.5.2)

• Drug induced liver injury is confirmed (refer to Section 5.5.3 for definition)

• Life threatening Infusion related reaction or hypersensitivity

• Grade <math>\geq 3</math> pneumonitis

Abbreviations: ALT = alanine aminotransferase; ANC = absolute neutrophil count; AST = aspartate aminotransferase; DILI = drug induced liver injury; INR = International normalized ratio; ULN = upper limit of normal.

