### 5.5.3 Potential Drug-Induced Liver Injury

Wherever possible, timely confirmation of initial liver-related laboratory abnormalities should occur prior to the reporting of a potential drug-induced liver injury (DILI) event. All occurrences of potential DILIs, meeting the defined criteria, must be reported as SAEs.

Potential drug-induced liver injury is defined as:

- ALT or AST elevation  $>3\times$  ULN; *and*
- Concurrent total bilirubin  $>2\times$  ULN, without initial findings of cholestasis (elevated serum alkaline phosphatase), *and*
- No other immediately apparent possible causes of aminotransferase (AT) elevation and hyperbilirubinemia, including, but not limited to, viral hepatitis, pre-existing chronic or acute liver disease or tumor(s), or the administration of other drug(s) known to be hepatotoxic

In general, an increase of AT to  $>3\times$  ULN should be followed by repeat testing within 48–72 hours of all four of the usual measures (ALT, AST, alkaline phosphatase, total bilirubin) to confirm the abnormalities and to determine if they are increasing or decreasing. Inquiry regarding symptoms should also be made (e.g., fatigue, nausea, vomiting, right upper quadrant pain or tenderness, fever, rash). Subjects may be retested locally, but normal laboratory ranges should be recorded and results made to the Investigator immediately. All data must be recorded in the CRF. If symptoms persist or repeat testing shows AT  $>3\times$  ULN for subjects with normal baseline measures or 2-fold increases above baseline values for subjects with elevated values before drug exposure, close observation should be initiated. If close monitoring is not possible, study drug should be discontinued.

Close observation includes:

- Repeating liver enzyme and serum bilirubin tests 2 or 3 times weekly. Frequency of retesting can decrease to once a week or less if abnormalities stabilize or the trial drug has been discontinued and the subject is asymptomatic.
- Obtaining a more detailed history of symptoms and prior or concurrent diseases
- Obtaining a history of concomitant drug use (including nonprescription medications and herbal and dietary supplement preparations), alcohol use, recreational drug use, and special diets
- Ruling out acute viral hepatitis types A, B, C, D, and E; autoimmune or alcoholic hepatitis; non-alcoholic steatohepatitis (NASH); hypoxic/ischemic hepatopathy; and biliary tract disease

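### Confirmed drug-induced liver injury stops study drug at first occurrence but is not a listed DLT, so some Part A cases would not enter the 3+3 count

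*Combined protocol and SAP*

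**What the plan says.** **Stopping rule.** Table 5-1 has a block headed "Toxicities Requiring Discontinuation of Investigational Product at First Occurrence". One of its four entries is "Drug induced liver injury is confirmed", with a pointer to Section 5.5.3. The entry carries no grade.

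**Definition.** Section 5.5.3 defines potential DILI as ALT or AST >3 x ULN with concurrent total bilirubin >2 x ULN, no initial cholestasis and no other immediately apparent cause. It adds: "All occurrences of potential DILIs, meeting the defined criteria, must be reported as SAEs".

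**DLT list.** Section 3.1.3 covers the first 3 weeks of Cycle 1. Two of its rows could reach a liver event. The row for laboratory values reads: "Clinically-significant Grade 3 or 4 non-hematologic laboratory abnormality that does not resolve to Grade 0/1 or baseline within 7 days". If the event is instead recorded as a clinical diagnosis, the row that could apply is this one: "Grade 3 or 4 non-laboratory AE with the exception of fatigue, asthenia, nausea, or other manageable constitutional symptom". Neither DILI nor discontinuation for toxicity is listed as a DLT.

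**Escalation.** Section 3.1.1 (text under Figure 3-1) says: "If 0 of 3 subjects experience a DLT in a cohort, the next dose level will be opened for enrollment". With 1 DLT in 3, three more subjects are treated; with 2 or more in 6, the MTD has been exceeded. For the chosen dose: "At least 6 subjects must be treated at the putative MTD or RP2D, with no more than 1 incident of DLT".

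**Discretion.** Section 3.1 says: "The SMC may recommend further evaluation of safety at a given dose level".

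**The concern.** The other three entries in the discontinuation block are Grade 4 photosensitivity or skin reaction, life-threatening infusion reaction or hypersensitivity, and pneumonitis of Grade 3 or higher. All are severe clinical events. At Grade 3 or 4 within the 3-week window they fall under the non-laboratory DLT row. DILI is the exception, because it is defined by two laboratory values read together, while the laboratory DLT row needs Grade 3 or 4, clinical significance and persistence beyond 7 days.

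The two rules also rank the event oddly. Under Section 5.2.4.1 a subject with a Cycle 1 DLT may receive more drug if there is benefit, the toxicity is managed and approval is given. Confirmed DILI ends treatment by default. An event with the stricter consequence for the individual can thus be missing from the count that decides whether the next subjects get a higher dose. With 3 to 6 subjects per level, a single event can change that decision.

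**Working it through.** The protocol states no DLT rate, DILI rate or 3+3 operating characteristics, so there is no planned figure to reproduce on this point. The check has three parts.

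**1. Which confirmed DILI cases miss the DLT list**

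Inputs: the DILI thresholds (Section 5.5.3); Grade 3 ALT/AST = >5.0-20.0 x ULN, Grade 4 = >20.0 x ULN, and bilirubin Grade 2 or higher = >1.5 x ULN (Table 5-1); the DLT rows (Section 3.1.3).

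- *Route A, enzymes below Grade 3.* ALT/AST of >3 to 5 x ULN meets the DILI enzyme limb but is below Grade 3. If bilirubin is also below Grade 3, no laboratory value can be a DLT, however long it lasts. The documents do not give the Grade 3 bilirubin cut, so it must be assumed. At >3 x ULN the affected bilirubin range is >2 to 3 x ULN. At >2.5 x ULN it narrows to >2 to 2.5. At >2 x ULN the route closes.
- *Route B, rapid recovery.* A Grade 3 or 4 liver value that returns to Grade 0/1 or baseline within 7 days is not a DLT. This follows from Section 3.1.3 alone.

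On either route the event becomes a DLT if the investigator grades the diagnosis as a Grade 3 or 4 non-laboratory adverse event.

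**2. What the 3+3 rule does with such a case**

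The drug is given once, on Day 1 of a 6-week cycle. A subject barred from further doses can still complete the 3-week window and count as evaluable without a DLT. A subject who leaves early for a non-DLT reason is replaced.

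| Events at the level | Count as written | Default action | Count if DILI is a DLT | Action |
|---|---|---|---|---|
| 1 uncounted DILI in 3, no DLT | 0 of 3 | open next level | 1 of 3 | treat 3 more |
| 1 uncounted DILI + 1 DLT in 6 | 1 of 6 | continue; within the MTD/RP2D limit | 2 of 6 | MTD exceeded |

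In the first row, counting the DILI means that escalation needs three further DLT-free subjects. With an assumed per-subject DLT rate p this has probability (1-p)³: 0.9³ = 0.729 at p = 10%, and 0.8³ = 0.512 at p = 20%. As written, the default is to escalate.

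**3. Effect before any data are seen**

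Let p be the per-subject probability of a counted DLT. The probability that a level opens the next one is

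f(p) = (1-p)³ + 3p(1-p)² × (1-p)³ = (1-p)³ + 3p(1-p)⁵.

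Example: f(0.10) = 0.729 + 0.3 × 0.59049 = 0.9061.

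Assumptions: other DLTs at 10% or 20% per subject; uncounted DILI at 1% or 2% per subject; the two mutually exclusive, so that counting DILI adds its rate to p.

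| Other DLTs | As written | DILI 1% counted | DILI 2% counted |
|---|---|---|---|
| 10% | f(0.10) = 90.6% | f(0.11) = 88.9% | f(0.12) = 87.2% |
| 20% | f(0.20) = 70.9% | f(0.21) = 68.7% | f(0.22) = 66.5% |

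The differences are 1.7 to 3.5 percentage points at 10% other DLTs, and 2.2 to 4.4 points at 20%. They apply at 0.2 and 0.3 mg/kg. No level is planned above 0.4 mg/kg, so there only the MTD/RP2D limit is affected.

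**The case against.** **Safeguards exist.** Every potential DILI is a serious adverse event, reported within 24 hours. The SMC meets routinely to review emerging safety and may hold a level for further evaluation. The MTD and RP2D are set after review of all available data, with at least 6 subjects treated. This stands as mitigation. But the SMC power is discretionary, the MTD review can come after the next level has opened, and neither makes the event count in the 3+3.

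**The diagnosis may be graded.** Section 8.1.2 requires a severity rating for every adverse event, with a fallback scale where CTCAE cannot be used. A DILI diagnosis rated Grade 3 or 4 as a clinical event would be a DLT with no 7-day allowance. That is correct and limits the point. The protocol does not say whether DILI is to be handled as a laboratory or a clinical event, so two sites could classify the same case differently.

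**The lists serve different purposes.** Discontinuation rules protect the individual, DLT rules govern escalation, and nothing requires them to match. The 7-day allowance is deliberate and recurs in Table 5-1. Yet Table 5-1 itself acts on Grade 3 ALT/AST combined with raised bilirubin at first occurrence, without a 7-day condition; Section 3.1.3 has no counterpart.

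**Stronger readings that the documents do not support:**
- *Any DILI stop in 3 subjects leads to escalation.* A clinically significant Grade 3/4 liver value that persists beyond 7 days in the window is already a DLT, as is a diagnosis graded 3/4. Onset after 3 weeks is outside the DLT rule altogether.
- *Every case meeting the Section 5.5.3 thresholds is a mandatory stop.* That section defines potential DILI and says only that stopping should be considered. Table 5-1 requires it once DILI is confirmed, a term the protocol does not define, and allows adjustment with Medical Monitor approval (Section 5.2.4.3).
- *Most DILI escapes, or escalation probabilities shift greatly.* The documents give no distribution of enzyme levels or recovery times and no DILI rate. Liver events are not among the frequent toxicities in Sections 1.2 and 1.4.

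**Conclusion.** The gap is real but limited. It concerns confirmed DILI with onset in the first 3 weeks of Part A, on Route A or Route B, and not graded by the investigator as a Grade 3/4 non-laboratory event. In those cases the default rule leaves a treatment-ending liver injury out of the DLT count.

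The average effect is small: 1.7 to 4.4 percentage points on the chance of escalation over the assumed rates. The effect on a level where a case occurs is not small, since the default moves from treating three more subjects to opening the next dose, or from MTD exceeded to MTD acceptable.

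The rule mismatch rests on the text alone, except that Route A also needs a Grade 3 bilirubin cut above 2 x ULN. All event rates are assumptions. The point is worth correcting because the remedy is nearly free, not because many cases are expected.

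**What to change.** Add one bullet to the DLT list in Section 3.1.3:

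*Drug-induced liver injury (ALT or AST >3 x ULN with total bilirubin >2 x ULN per Section 5.5.3) confirmed on repeat testing with no alternative cause found on work-up, regardless of grade or duration.*

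The bullet should be tied to confirmed DILI, as above. Counting every potential case would go beyond the mismatch with Table 5-1.

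Cost: no new assessments. Chemistries are already drawn on Days 8 and 15 (Section 6.3.5), and repeat testing at 48-72 hours and the work-up for other causes are already in Section 5.5.3. The downside is an occasional expansion to 6 subjects or an earlier end to escalation. Planned Part A size is unchanged, because Section 10.1 already assumes 6 subjects at each of 3 levels in 8 disease cohorts: 3 × 6 × 8 = 144.

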### 5.3 Required Premedication and Postmedication

All subjects enrolled will receive premedication consisting of dexamethasone orally (PO) at 8 mg twice daily given on Day -1, Day 1 (the day of dosing), and Day 2 of each cycle. Dexamethasone will be provided through a subject's local prescription by Investigator or other provider (i.e., dexamethasone will not be provided by the Sponsor). When dexamethasone is not available, the glucocorticoid-equivalent dose of an alternate corticosteroid may be administered. Parenteral (e.g., IV) administration may be substituted for PO at the discretion of the Investigator.

### 5.4 Concomitant Therapy

All concomitant medications, blood products, procedures and radiotherapy administered will be recorded from Day 1 (predose) through the safety reporting period ([Section 7.2](#) and [Appendix 13.1](#)). Any concomitant therapy given for a study protocol-related AE should be recorded from the time of informed consent.

#### 5.4.1 Required Concomitant Therapy

Other than dexamethasone ([Section 5.3](#)), there are no required concomitant therapies. However, due to the potential for rovalpituzumab tesirine-related skin photosensitivity, subjects should be advised to avoid unprotected sun exposure and use a broad spectrum sunscreen (sun protection factor [SPF] of at least 30), protective clothing, a broad-brimmed hat, and sunglasses when outdoors or when driving or riding in the car for more than 1 hour, with re-application of sunscreen as activity-appropriate.

#### 5.4.2 Allowed Concomitant Therapy

Standard supportive care for drug-related toxicity is permitted, including growth factors and blood product transfusions in accordance with local institutional standards. Other standard supportive care for symptom control or drug-related toxicity is allowed, such as analgesics, anti-emetics, electrolyte replacement, and hydration. Bone modifying agents for bone metastases are also permitted in accordance with local institutional standards. Other prescribed medications for non-neoplastic conditions are allowed, as well as vitamins and nutritional supplements.

Further ongoing treatments may be permitted for prostate cancer subjects according to [Appendix 13.7](#).

Concomitant prednisone (or equivalent) may be used at a dose of  $\leq 20$  mg/day. The use of intermittent high-dose corticosteroid treatment to prevent or manage hypersensitivity reactions, serosal effusions (refer to [Section 5.5.1](#)), or other non-cancer-related symptoms, including premedication for known hypersensitivity reactions to contrast for scans is allowed.

Routine prophylaxis with vaccines is permitted; however, vaccines used should not contain live micro-organisms.

If the subject is taking chronic suppressive anti-infectives (antiviral, antifungal, or antibacterial), appropriate investigation must be completed prior to registration and documentation must exclude active infection. The subject should continue suppressive anti-infectives for the duration of study participation.

Palliative radiation therapy is permitted. Study drug must be held during therapy. If more than 6 weeks have elapsed since the previous dose of study drug, the subject should undergo a radiographic tumor assessment before restarting study drug. If PD is detected in new sites, the subject will be required to discontinue study treatment (but may be eligible for re-treatment according to [Section 3.1.4](#)).

#### **5.4.2.1 Treatment of Isolated Central Nervous System Progression**

In the event of isolated CNS progression during study treatment, study drug may be withheld while palliative treatment is administered, e.g., a standard course of whole brain radiotherapy or stereotactic radiosurgery (SRS) in accordance with institutional practice, and restarted within 1 week after completion of radiotherapy. During this time the subject should be fully evaluated for other sites of progression. If more than 6 weeks have elapsed since the previous dose of study drug, the subject should undergo a radiographic tumor assessment before restarting study drug. If additional sites of PD are present, the subject will be required to discontinue study treatment (but may be eligible for re-treatment according to [Section 3.1.4](#)).

#### **5.4.3 Prohibited Concomitant Therapy**

Subjects may not receive other investigational drugs, immunosuppressive medications, or systemic anti-neoplastic therapy during the study, other than as allowed in [Sections 4](#), [5.2.4](#), and [5.4.2](#), and [Appendix 13.7](#).

### **5.5 Management of Adverse Reactions**

#### **5.5.1 Serosal Effusions**

Serosal effusions (pleural or pericardial, or ascites) have been observed with rovalpituzumab tesirine, and have the potential to be life-threatening (e.g., pericardial tamponade). Therefore,

development of any of these events, or worsening from baseline, warrants prompt evaluation by the Investigator or designee. Cytology analysis should be done for pleural and pericardial effusion as appropriate. Alternative causes, such as infection, congestive heart failure, or PD, should be ruled out. When appropriate, a unifying diagnosis or reached diagnosis should be reported (e.g., “heart failure,” not simply “pleural effusion” and “edema limbs”). When considered clinically significant (e.g., Grade 2 or higher and considered related to study drug):

- Systemic corticosteroids, when initiated promptly, have been reported to be beneficial in some prior cases. The Investigator should consider a tapering regimen, such as dexamethasone up to 8 mg orally twice a day for 5 days, followed by 4 mg orally twice a day for 5 days, then 2 mg orally twice a day for 5 days. Alternatively, nonsteroidal therapies for serositis may be considered, such as non-steroidal anti-inflammatory drugs (NSAIDs, e.g., ibuprofen 400–600 mg orally 3 to 4 times daily) or colchicine (e.g., 0.6 mg orally 2 to 3 times daily) given for 1–2 weeks.
- Until clinical experience suggests otherwise, guidance for dose delay and/or reduction, as well as criteria for ongoing dosing, should follow [Section 5.2.4](#).

